Hypothesis 2: Post-hypoxic former preterm children will exhibit reduced activity within cortical networks innervated by the SNpc and VTA when compared to healthy controls.

Background

1. *Describe the relevant prior experience and gaps in current knowledge describing how it will add to existing knowledge.*
2. *Describe any relevant preliminary data.*
Please add relevant references at the end of the protocol, not at the end of this section.

Hypoxic insults occurring during the perinatal period remain the leading cause of permanent brain impairment.¹ Apparent cognitive and motor dysfunction, such as that

seen in cerebral palsy, will occur in 4-10% of those post-hypoxic newborns.^{2,3} Subtle impairment, such as that seen in disorders of minimal brain dysfunction will occur in > 3 million post-hypoxic newborns.^{4,5} Collectively, hypoxia-induced morbidity and mortality afflicts 3% of all newborns, worldwide, and leads to substantial personal and socioeconomic burden.⁶

Specific neuropathology, elicited by subtle hypoxic insults that lead to cognitive dysfunction, is not well described in humans. Over 84% of preterm infants experience apnea of prematurity with accompanying intermittent hypoxia.^{7,8} Neuropathology, cognitive impairments, and motor impairments induced by *severe* hypoxic insults are well described⁹ and frequently lead to a clinical diagnosis of cerebral palsy.^{6,10} Cognitive and motor deficits are also associated with *mild to moderate* hypoxic insults,¹¹ but the specific neuropathology is poorly defined. Mild to moderate hypoxic insults resulting from apnea of prematurity do not elicit the overt neuropathology observed following severe hypoxic events. As such, standard neuroimaging and diagnostic techniques,¹² with the exception of positron emission tomography requiring infusion of radioactive ligands,¹³ have failed to identify major changes in brain structure or function. Nonetheless, disorders of minimal brain dysfunction and cognitive impairments do exist.¹⁴⁻¹⁶

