If they continue to express interest in study participation, we will determine if they meet study inclusion criteria (e.g. we will ask them if the child is between 9 and 17 years old; how close to the due date the child was born; if the child would be able to play a board game and push a button during a memory game). Then we will determine if they have any exclusionary criteria including a history of epilepsy, autism, or previous history of concussion requiring medical treatment. We will also assess for any contraindications to MRI scans. We will ask them if they have a cardiac pacemaker, intracranial aneurysm clips; intravascular shunt; dental devices such as braces or dentures; metallic implants or external clips within 10 mm of the head; implanted metallic devices such as pumps or previously implanted neurostimulation devices; cochlear implants, defibrillators, pacing wires, body piercings that cannot be removed; metal filings such as shrapnel; tattoos on the head and neck; or a history of claustrophobia, or a current pregnancy (if female).

If they meet inclusion criteria and do not possess any exclusionary criteria, one of the certified research team members will schedule an appointment with the child/parent to obtain written informed assent and consent.

2. Describe the criteria that define who will be **included** in your final study sample.

	Inclusion
1.	For Study Group Children: Birth gestational age between 22-30 weeks and birth weight appropriate for gestational age (AGA).
2.	For Healthy Control Children: Birth gestational age \geq 38 weeks gestation and birth weight appropriate for term gestation within the age range of the eligible former preterm children.
3.	Ability of the child to provide assent, with the parent/legal guardian able to provide written informed consent for study procedures.
4.	Sensory and motor capability to complete study tasks (i.e. Grooved Pegboard test; verbal n-back memory test).

3. Describe the criteria that define who will be **excluded** in your final study sample.

	Exclusion
1.	Mental Development index < 80 at 2-year follow-up for preterm cohort.
2.	Past history of concussion requiring medical treatment to avoid confounding of MRI

	data.
3.	Current history of epilepsy to avoid confounding of EEG data.
4.	Current diagnosis of autism.
5.	Child who suffers from claustrophobia (per parent report).

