6.	Child unable to participate in neuroimaging due to claustrophobia or medical contraindication to MRI including any implanted medical device, dental braces, surgical clips for aneurysms in the head, heart valve prostheses, electrodes or other metallic objects; pregnancy
7.	Healthy control children who were treated in the Neonatal ICU during the newborn period for breathing difficulties.
8.	Healthy control children who were hospitalized for breathing problems in the first 3 months of infancy.
9.	If the child is suffering from an acute illness, he or she will be temporarily deferred.

Number of Research Participants

- Indicate the target number of research participants to be accrued locally.*
 Our goal is to obtain 30 complete data sets (preferably Study group = 20; Healthy control = 10). Due to movement artifact in the MRI, some scan data may not be usable so we may need to enroll up to 35 participants. We may also conduct repeat studies on a subset of up to 5 children (~15%) to establish reproducibility of collected data. Only subjects who checked "yes I agree to be contacted..." on their first signed parent consent form will be approached by phone to ascertain interest in participating in the study a second time. Participants studied twice will be re-consented for the second data collection session.
- If this is a multi-site study, indicate the total number of research participants to be accrued across all sites.*
 N/A

Vulnerable Populations

- Indicate specifically if you will include each of the following special populations by checking the appropriate box:*

 - Adults unable to consent**
 - Minors (infants, children, teenagers)**
 - Wards of the state
 - Foster Children
 - Pregnant Women**
 - Neonates**
 - Neonates of Uncertain Viability**
 - Employees of CWRU or UHHS**
 - Prisoners**
 - Illiterate Individuals**
 - Non-English Speaking**
 - University Students**

- If the research involves individuals that are included in a vulnerable population, describe the additional safeguards included to protect the rights and welfare of the individuals for each population indicated.*

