The flyer will indicate that we are conducting a study on brain activity in school age children and that we wish to enroll a broad representation of children. Parents would then be asked to contact us if they would be interested in taking part in the study. This strategy would allow us access to a large pool of potential controls who meet eligibility requirements. Using an IRB-approved telephone script, our research staff will then contact the parents of the child. The purpose of the telephone call will be to further explain the study to the parents, confirm their interest in taking part, and determine their child's eligibility. We are prepared to discuss any aspect of a child's participation at greater length, including research participant rights. Telephone numbers of the study PIs are provided to those asking for more or different information.

The term-born healthy control participants are selected based on eligibility criteria (between 9 and 17 years old; without diagnosis of autism, epilepsy, metallic implants, dental braces, or those who've been treated for a concussion) and approximately matched to study children based on age. All healthy control candidate participants will have been of normal birth weight (> 2500 grams) and with gestational age > 37 weeks.

Additionally, we will exclude children from the healthy control group if they were treated in the neonatal ICU during their birth hospitalization for breathing problems or were hospitalized for breathing problems in the first 3 months of infancy. Children in special education programs will not be excluded as controls. Both groups of children are expected to be in generally good physical health, although we anticipate that the group of preterm-born children may have more chronic conditions (e.g. asthma) and more health-related functional limitations than the term group.

Setting

1. *Describe the sites or locations where your research team will conduct the research.*
2. *Identify where your research team will identify and recruit potential research participants.*
3. *Identify the physical location where research procedures will be performed.*

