Our consent forms explain the nature of all procedures using lay terminology, and we stress that participation is voluntary. Our research assistants and Co-PIs are available to answer questions. One of the study investigators ([name] or [name]) is also available to answer questions about the study at other times. All activities are compliant with local IRB and HIPAA guidelines, such as destroying all pre-screening forms and obtaining verbal permission, as appropriate, for phone interviews. At the beginning of the study, and then periodically, any IRB, HIPAA or privacy requirements that may be in effect at that time also will be checked to assure that study procedures are compliant with current rules. With permission from the parent, the health care provider for consented eligible children are contacted to identify/clarify any exclusionary criteria.

Additional Considerations for Consent Process with Adults

Non English Speakers

- *If research participants who do not speak English will be enrolled, describe the process to ensure that the oral and written information provided to those research participants will be in that language during initial consent as well as throughout the study. Indicate the language that will be used by those obtaining consent.*
- *List the language(s) other than English that will be included.*

Eligible study participants (children or their parent) who are not fluent in English will not be excluded. We will submit a translated version of the informed consent form to the IRB for approval prior to use. Only a UH-based certified professional translator who is fluent in both English and the child's/parent's language will conduct the informed consent. Other study related documents and procedures that need to be completed by the child or parent will be translated into the participant's native language. We will include any languages for which a UH-based certified professional translator is available.

Adults Unable to Consent

- *Describe the process to determine whether an individual is capable of consent.*
- *List the individuals from whom permission will be obtained in order of priority (e.g. durable power of attorney for health care, court appointed guardian for health care decisions, spouse, and adult child).*

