- Health plan beneficiary number
- Account number
- Certificate/license number
- Any vehicle or other device serial
- Device identifiers or serial numbers
- Web URL
- Internet protocol (IP) address
- Finger or voice prints
- Photographic images
- Other: Any characteristic that would uniquely identify the individual

2. *List all other data to be collected for the research study (e.g. laboratory values, physician notes, length of stay, etc.).*

- Magnetic Resonance Imaging, specifically T1 structural scan, Diffusion Tensor Imaging (DTI), and functional Magnetic Resonance Imaging-Blood Oxygen Level Dependent (fMRI-BOLD)
- High density electroencephalography (HD-EEG)

- Neurobehavioral Assessments of child: Verbal n-back; Grooved Pegboard task
Parent report of child behavior (parent-report): Child Behavior Checklist, Vanderbilt Assessment Test, Child’s Sleep Habits Questionnaire (for children ages 9-12), Pediatric Sleep Questionnaire (for children ages 9-17).
- Urine collection (to determine pregnancy exclusion for female child participants)

Data Analysis Plan

1. Describe the data analysis plan, including any statistical procedures. Provide a power analysis if applicable.
2. If applicable, describe the primary and secondary study endpoints including safety endpoints.

Our intent in this exploratory cross-sectional two-arm pilot study is to develop sufficient Scientific Rigor to support a future study appropriately powered to account for our proposed primary outcome measures and co-variates. Our sample will include 20 prematurely born children who experienced hypoxic insults during postnatal life. To allow comparison to “normative” expectations, we will compare these 20 former preterm children with 10 healthy term-born controls without exposure to hypoxia and of similar age, sex, race distribution as the preterm group. Data from these 30 children will be used to develop appropriate sample sizes, using actual rather than predictive data, for future studies characterizing neural structure and function following postnatal hypoxic insults.

Specific structural and functional characteristics used in our analyses will include

- apparent diffusion coefficients and fractional anisotropy generated from DTI data
- fMRI-BOLD, measured during the pediatric verbal n-back, and HD-EEG sLORETA

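### Term controls are described as unexposed to hypoxia, but the control exclusions cover only breathing-related care, so a child with diagnosed perinatal hypoxia and no such care can enter the reference group

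*Combined protocol and SAP*

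**What the plan says.** The Data Analysis Plan describes the reference group as "10 healthy term-born controls without exposure to hypoxia", similar to the preterm group in age, sex and race. Under Study Design, Procedures and Timeline, the question is whether differences in birth events and in newborn oxygen levels lead to impairment of dopaminergic pathways.

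Two control exclusions bear on early hypoxia:

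- Exclusion 7: "Healthy control children who were treated in the Neonatal ICU during the newborn period for breathing difficulties".
- Exclusion 8: "Healthy control children who were hospitalized for breathing problems in the first 3 months of infancy".

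Recruitment Methods, item 5, repeats them with the same scope: children "treated in the neonatal ICU during their birth hospitalization for breathing problems", or hospitalized for such problems in early infancy. Control inclusion requires term gestation and "birth weight appropriate for term gestation within the age range of the eligible former preterm children"; it names no perinatal event.

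The prescreening text mentions "a history of epilepsy, autism, or previous history of concussion requiring medical treatment", followed by MRI contraindications. After consent, and with the parent's permission, "the health care provider for consented eligible children are contacted to identify/clarify any exclusionary criteria". In the Data Analysis Plan, the covariate for frequency of hypoxic insults is defined within the preterm group only.

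**The concern.** Hypoxia is the exposure under study, so the exposure status of the reference group should follow from the eligibility criteria or be measured. Here it is asserted. The Background opens with the statement that "Hypoxic insults occurring during the perinatal period remain the leading cause of permanent brain impairment", and the design section counts birth events as part of the exposure. A term child with a hypoxic event at birth is therefore exposed in the plan's own terms.

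An affected child in a group of 10 would pull the control mean towards the preterm mean and make the difference look smaller. The plan intends to use these data to set sample sizes for later studies, so a diluted difference would carry forward into them.

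**Working it through.** **1. Which children can enter.** The plan has no figure to reproduce here, so the check sets the stated exposure status against each criterion or procedure that could secure it.

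| Provision | Does it remove a term child with perinatal hypoxia? |
|---|---|
| Control inclusion (gestation, birth weight, age) | No |
| Exclusion 7 | Only if NICU treatment was for breathing |
| Exclusion 8 | Only if hospitalized for breathing in the first 3 months |
| Epilepsy, autism, concussion, MRI and other general exclusions | Only if one of these is also present |
| Provider contact | No; it serves the listed exclusions, and perinatal hypoxia is not one |
| Focused neurological history and examination | No hypoxia rule is attached |
| Withdrawal for exclusions found late | No; it also depends on the listed exclusions |
| Hypoxia covariate | No; it is defined within the preterm group only |

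The remaining gap is a child with diagnosed birth asphyxia or perinatal hypoxia and no breathing-related NICU or hospital care. The recruitment text mentions parent questions on health history, but the List of Data to be Collected contains only behaviour and sleep questionnaires, so no listed item records birth events in controls.

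**2. Dilution.** Inputs: 10 controls and 20 preterm children (Number of Research Participants). Assumption: k exposed controls each carry the full preterm deficit.

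Expected difference = true difference × (1 − k/10)

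- k = 1: × 0.90
- k = 2: × 0.80

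The plan states no effect size. For an assumed gap of 0.8 SD, the results are 0.8 × 0.90 = 0.72 SD and 0.8 × 0.80 = 0.64 SD.

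**3. Power, for scale.** The plan's significance level is 10%; two-sided is assumed, in line with the 90% intervals. Using the normal approximation, the difference detectable with 80% power is (1.645 + 0.842) × √(1/10 + 1/20) = 0.96 SD. Under the same full-deficit assumption:

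- k = 1: 0.87 SD, power 72%
- k = 2: 0.77 SD, power 64%

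A later sample size scales as 1/(difference)². It would be inflated by 1/0.90² = 1.23 for one such control and 1/0.80² = 1.56 for two.

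**4. How likely.** The share p among eligible volunteers is not given. The chance of at least one in 10 is 1 − (1 − p)¹⁰: 9.6% at p = 1%, 18.3% at 2% and 26.3% at 3%. The Background's 3% refers to all newborns worldwide and includes deaths, so it is probably high for healthy term survivors. At p = 3% the expected dilution is 3%, which takes 0.80 SD to 0.80 × 0.97 = 0.776 SD.

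**5. Against sampling error.** The 90% interval half-width for an unadjusted difference is about 1.70 × √(1/20 + 1/10) = 0.66 SD. One fully affected control moves an assumed 0.8 SD gap by 0.08 SD.

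**The case against.** The strongest reply is that the plan studies mild to moderate postnatal hypoxia, measured over the first 8 weeks, and that exclusions 7 and 8 cover this with a longer window of 3 months. Read this way, the description of the controls largely matches the criteria. This carries weight but does not close the gap, because the design section names birth events alongside newborn oxygen levels.

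Other parts of the reply stand and limit the point:

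- A reader might infer that birth asphyxia in general slips through. It does not: asphyxia treated in the NICU for breathing difficulty is caught by exclusion 7.
- A reader might infer that any NICU stay marks an exposed control. NICU care for another reason is not in itself hypoxia. Excluding all such children would select unusually healthy controls and could inflate the difference.
- A reader might infer from the prescreening text that birth history is never asked. The text gives its questions as examples and leaves out exclusions 7 and 8 themselves. The script is a separate document, so its content cannot be judged from this summary.
- The general exclusions, the expectation of good physical health and the neurological examination make a markedly affected control less likely, although none is a hypoxia criterion.

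**Conclusion.** The point holds in a limited form. The criteria do not deliver the stated exposure status of the controls, and no listed data item would reveal an exposed control. That conclusion rests on the text alone.

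The size is conditional. Each exposed control costs 10% of the expected difference only if that child carries the full deficit of a child born at 22 to 30 weeks, which the documents do not show. The number of such children may be zero, and the likely effect is small beside the sampling error of a 30-child pilot. A reader might conclude that both hypotheses are biased towards no difference; the documents support only the possibility. Nor does the plan say that controls are coded as having zero exposure in the regression.

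**What to change.** Add a control exclusion for parent-reported or recorded birth asphyxia or perinatal hypoxia. Put the question in the control prescreening script, and check it through the provider contact already described in the consent-waiver section. Do not widen it to any NICU admission.

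The cost is one criterion, one question and an occasional volunteer turned away, from a pool of potential controls that Recruitment Methods calls large. Parent report can miss an event, and the provider check depends on the parent's permission, so some uncertainty would remain.

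If the sponsor prefers the present criteria, reword the Data Analysis Plan to describe the controls as without known breathing-related NICU or hospital care in early infancy. That costs no participants and makes the description match what is screened.

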Purpose: Our goal is to characterize structure and function of dopaminergic pathways and the cortical regions innervated by those pathways in post-hypoxic former preterm children. We hypothesize that dopaminergic projections, originating in the substantia nigra pars compacta (SNpc) and ventral tegmental area (VTA), projecting primarily to the striatum and prefrontal cortex (PFC) to modulate motor control and cognitive function, will be structurally and functionally impaired. Our primary study cohort is comprised of former preterm children born in 2004-2010 with birth gestational age between 22-28 weeks in whom we have characterized their postnatal hypoxic exposure continuously during their first eight weeks of life. To meet recruitment targets, we may additionally recruit additional former preterm children born between the ages of 9 and 17 years old at consent, with birth gestational age between 22-30 weeks and birth weight appropriate for gestational age (AGA). For comparison, we plan to also recruit healthy control children based on eligibility criteria (between the ages of 9 and 17 years at time of consent; without diagnosis of autism, epilepsy, metallic implants, dental braces, or those who have been treated for a concussion), and who are within the age range of the eligible former preterm children at the time of consent.

Specific Aim 1: We will quantify and compare the structural integrity of dopaminergic circuits originating in the substantia nigra pars compacta (SNpc) and ventral tegmental area (VTA) that project to striatum, prefrontal cortex, and nucleus accumbens, in post-hypoxic former preterm children versus healthy control children born at term within the age range of the eligible former preterm children.

Specific Aim 2: We will quantify and compare functional activity during tasks that engage executive function within cortical brain regions of post-hypoxic former preterm children versus healthy control children born at term within the age range of the eligible former preterm children at the time of consent. Our emphasis will be upon the prefrontal cortex which receives projections from the SNpc and VTA.

Hypothesis 1: Post-hypoxic former preterm children will manifest significantly reduced white matter density within dopaminergic circuits originating from the SNpc and VTA when compared to healthy controls.

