2. *Describe the methods that will be used to identify potential research participants.*

The proposed study will involve participation of male and female children to achieve a total number of 30 complete data sets. All children to be studied will range in age between 9-17 years during the funding period. Study participants will include survivors of preterm birth, with birth gestations of 22-30 weeks and birth weights appropriate for gestational age.

We intend to focus our recruitment on 20 children who were born preterm with birth gestational ages between 22-30 weeks, are survivors from Rainbow Babies & Children's Neonatal Intensive Care Unit, and have been followed since birth. The children invited for participation will be part of the maintained cohort for whom continuous oxygen saturation data were collected in their first 8 weeks of postnatal life. Co-Investigator [name] maintains this research cohort. In the event that we cannot enroll 20 children who have continuous oxygen saturation data from their neonatal hospital stay, [name] will assist us to identify other preterm survivors who are similar to the study group population but may be between 9 and 17 years old and/or have birth gestations up to 30 weeks. We will also recruit for other preterm survivors via study flyers and advertisements.

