Twitter: Study investigators will post their flyer on Twitter accounts operated by investigators and CWRU-owned and operated accounts. Individual Twitter users will be able to retweet and reply to investigators. Investigators and account owners will respond by directing families to our contact information on the flyer.

ResearchMatch.org: The study will be posted on ResearchMatch.org so that families searching for research studies can view our study title and contact information.

Recruitment language to be used on ResearchMarch.org: [name] and [name] at CWRU, and [name] at Rainbow Babies and Children’s Hospital are looking for families to participate in a study on brain development. The study involves one 3-hour visit to the CWRU/University Hospitals campus where a research team will measure brain activity. First, children will lie quietly for about 30 minutes in the MRI scanner while playing a visual task-response game. After the MRI scan, brain activity will again be measured with EEG. This involves having the child wear a stretchy cap while playing the visual task response game and completing a pegboard puzzle. Parents will complete questionnaires about the child’s health history, behavior, and sleep. Both parents and children will be compensated for their time. The investigators are especially seeking children who were born prematurely (gestation 22-30 weeks) and also children who were born full term (gestation 38-41 weeks). Children with epilepsy, autism, medical implants, dental braces, or those who have been treated for concussion are not eligible. Please call [contact] for more information.

The CWRU Daily: We plan to advertise our study on the CWRU Daily. The submission to the Case Daily is attached to this modification. Interested families are instructed to contact the study investigators.

TriNetX: Research personnel will work the with TriNetX personnel to identify families who meet eligibility requirements. Researchers will then use the approved email template to contact families as well as phone scripts for communication. We will call families a total of 3 times and leave a voicemail if they do not pick up our phone call. The original application to IRB requested a HIPAA waiver authorization and we will continue to utilize this authorization to work with the TriNetX team.

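### The controls are called similar in age, sex and race, but recruitment matches only roughly on age, adjustment depends on a significance screen, and family background is not in the listed data

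*Combined protocol and SAP*

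**What the plan says.** **Comparability assumed.** The Data Analysis Plan describes the comparison group as "healthy term-born controls without exposure to hypoxia and of similar age, sex, race distribution as the preterm group".

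**Comparability secured by recruitment.** The Purpose section admits controls "who are within the age range of the eligible former preterm children at the time of consent". The inclusion table asks for "birth weight appropriate for term gestation within the age range of the eligible former preterm children". Recruitment Methods, item 5, adds that controls are "approximately matched to study children based on age". No quota, stratum or match on sex or race appears.

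**Sources.** Preterm children are sought first from a hospital NICU cohort followed since birth. Recruitment Methods, item 1, says that advertisements and flyers serve particularly to recruit controls. Item 2 lists the routes, among them flyers that preterm families pass to other families, clinic and community postings, social media and a university newsletter ("We plan to advertise our study on the CWRU Daily").

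**Adjustment.** The regression has birth group as its main covariate. It adjusts for age, sex, race and frequency of hypoxic insults only where their confounding is significant, a term left undefined. The two-group tests at the 10% level are unadjusted. The group coefficient is then read as the difference caused by preterm versus term birth.

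**Family background.** Neither the List of Data to be Collected nor the covariate list names parental education, income or a similar measure.

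**The concern.** In an observational comparison, the group coefficient stands for preterm birth only as far as the groups are alike in other respects or the differences are modelled. Two gaps remain.

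First, similarity in sex and race is stated but not arranged, and similarity in age is arranged only loosely over a range in which children are still maturing. The regression can correct for these three, but the plan lets a significance result decide whether it does.

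Second, the two groups are reached mainly by different routes. If they differ in family background, the listed data allow nobody to see the difference or correct for it afterwards.

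The stakes are practical even for a pilot, because the plan says that these 30 children will supply the figures for sizing later studies. An effect estimate that carries some confounding would carry it into that calculation.

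**Working it through.** **Inputs from the documents.** Number of Research Participants: "Our goal is to obtain 30 complete data sets (preferably Study group = 20; Healthy control = 10" in parentheses, so 20 + 10 = 30. The plan gives no power, effect size or SD, so there is no further figure of its own to reproduce. Recruitment Methods, item 2: "All children to be studied will range in age between 9-17 years during the funding period". Significance level 10%, taken as two-sided to agree with the 90% confidence intervals.

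**Assumed inputs.** Ages uniform over the range; half of each group girls; confounder-outcome correlation r of 0.2-0.5; systematic group gap in a confounder of 0-1.0 SD; significance for confounding judged at 10%.

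**1. Standard error of the group difference, in SD units.** sqrt(1/20 + 1/10) = sqrt(0.15) = 0.39.

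**2. Chance gap in mean age with no matching.**
- Ages 9 to 17: SD = 8/sqrt(12) = 2.31 years. SD of the gap = 2.31 x 0.387 = 0.89. P(gap above 1 year) = 26%.
- Ages 9.0 to 17.99: SD = 9/sqrt(12) = 2.60. SD of the gap = 1.01. P = 32%.

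These are upper guides. If each control lies within 1-2 years of an index child, the probability falls to about 10-12% when index children are picked at random, and below 1% when they are spread across the preterm ages.

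**3. Chance gap in sex share.** With binomial counts out of 20 and 10 at 0.5, P(gap of 20 points or more) = 37% and P(30 points or more) = 16%. No rule in the plan lowers these.

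The figures in 2 and 3 show how easily the description of similar groups could be untrue. They are not biases. With no systematic gap, the unadjusted test kept its nominal error in simulation (9.9-10.2%).

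**4. What the significance screen does when there is a systematic gap.** Simulation of 20 versus 10 with no true group effect, 5,000 runs per setting, gaps of 0.5-1.0 SD, r = 0.2-0.5:

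| Analysis | Bias (SD) | False-positive rate |
|---|---|---|
| Unadjusted | 0.10-0.50 | 11-35% |
| Adjusted if covariate is associated with outcome | 0.02-0.11 | 11-16% |
| Adjusted if covariate is imbalanced between groups | 0.01-0.10 | 9.5-10.5% |
| Always adjusted | within about 0.02 | about 9-10% |

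The screen is weak: a 10% test of imbalance picks up a true 0.5 SD gap only about 36% of the time. For age, 0.5 SD is 0.5 x 2.31 = 1.2 years and 1.0 SD is 2.3 years, so the upper rows are unfavourable cases if age matching is carried out.

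**5. Family background.** Bias is roughly the group gap times the effect per SD. With an assumed gap of 0.3-0.8 SD and an assumed effect of 0.2-0.4 SD per SD, it runs from 0.3 x 0.2 = 0.06 to 0.8 x 0.4 = 0.32 SD. Divided by 0.39, that is 0.15 to 0.83 of a standard error. No documented input fixes these values or their direction.

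**The case against.** **Age, sex and race are already covariates.** This stands, and it is the main safeguard. A reader might infer that maturation and sex pass unchecked as a preterm effect; the regression plan does not support that. What remains is narrower: the screen, its undefined criterion and the unadjusted tests.

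**Adjustment at this size is extrapolation.** A reader might infer this too, but it goes too far. When simulated free draws happened to give a mean-age gap above 1 year, about 88% of controls still lay inside the preterm age range, and with a linear age effect the adjusted bias was about zero.

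**The sources are not separate.** This stands in part. Flyers passed on by preterm families are a named control route, Research Participant Compensation allows siblings, and the ResearchMatch text seeks preterm as well as term children. The newsletter notice is not stated to be for controls alone. Some social matching may follow, but none of it is required or measured.

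**Family background might be captured elsewhere.** Parents also answer questions on the child's health, and those forms are not shown. An item could be there, but no analysis of one is planned.

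**It is an exploratory pilot, and the assumed bias is below one standard error.** Both are true. They limit the weight of the point. They do not make an uncollected confounder recoverable.

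**Conclusion.** The point holds in limited form. The similarity in sex and race that the analysis section states has no mechanism behind it, and similarity in age rests on approximate matching. Imbalance in age, sex and race is partly handled: under the assumed gaps, screened adjustment leaves a bias of 0.01-0.11 SD, where always adjusting leaves about 0.02 SD or less. Family background is the larger gap in kind, because on the listed data it can be neither shown nor adjusted. Its size and direction are unknown, and 0.06-0.32 SD is an illustration from assumed inputs.

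The 26-32% age figure should not be read as what the plan will produce, since it ignores the plan's own age matching. Nor do the documents show that the groups differ in family background. They show only that such a difference would go unseen. The changes are worth making because they cost little.

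**What to change.** 1. Add one item on highest parental education to the form that the parent already completes during the scan. Report it by group and add it to the group model as a sensitivity analysis.
2. Keep age and sex in every group model whatever their significance, and tabulate age, sex and race by group.
3. At the existing telephone screen, balance controls on sex and on broad age band, at about one control per two preterm children, where feasible. Treat these as two separate margins: crossing three age bands with sex would leave 10/6 = 1.7 controls per cell. If balancing is not feasible, remove the similarity statement from the Data Analysis Plan.
4. Describe the group coefficient as an association with preterm birth, not as a difference caused by it.

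**Cost.** One more questionnaire item and possibly a few willing controls deferred. Age and sex take residual degrees of freedom from 28 to 26, and the education item, entered as one term, takes the sensitivity model to 25.
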